National guidelines that aid health care providers in determining a patient's eligibility for hospice and EOL option discussions are available, and several national organizations recommend guidelines for the institution of palliative care. The *inpatient* e-EOL algorithm operationalizes the application of hospice guidelines and clinical experience by ‘flagging’ those individuals with advanced cancer meeting guideline criteria for hospice eligibility; however, the *outpatient* e-EOL algorithm will target patients who are earlier in the cancer disease trajectory and would benefit from early palliative care consultation. The preliminary *inpatient* e-EOL algorithm was based on simple ICD-9 codes from the index admission (cancer, metastasis) and albumin measurements; however, UTSW, Parkland and all of their affiliated clinics adopted ICD-10 on October 1, 2015, and the algorithm is now being tested using these updated codes. The *outpatient* algorithm will harness a broadened range of factors contained in discreet fields from the EMR including: patient characteristics (age, race), initial determination of metastatic cancer diagnosis (stage III or IV disease), medications to treat pain and other cancer-related symptoms (opioids/NSAIDs/steroids, anti-emetics, appetite stimulants, antidepressants), processes of care (chemotherapy, radiation therapy), as well as number of ED visits, hospitalizations and ICU stays related to the primary cancer diagnosis. *Albumin < 2.5 mg/dl will not be used in this algorithm as it is a marker of poor prognosis, and we hope to detect patients with metastatic disease earlier in their disease trajectory.* We will explore the impact of different types of Boolean logic combining these factors. We will also broaden our net to include ICD-10 codes in diagnosis, problem lists, and encounter fields of all prior inpatient and outpatient encounters in the past 12 months. Our goal is to increase have sensitivity of the inpatient algorithm of 40-50% and specificity of >90%.

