and “negative” cases to help them develop a shared understanding. Once the training is completed, two reviewers will independently review the EMR for each case and render a final judgment about whether the patient: 1) has Stage III/IV breast, lung, colon, prostate or other advanced cancer, and 2) meets guideline criteria for being eligible for an EOL care options discussion. Initial agreement and Kappa scores will be computed, and areas of disagreement will be resolved by discussion. The third reviewer will be used if consensus cannot be reached. Sensitivity, specificity, and positive/negative predictive values for the algorithm will be calculated. The e-EOL algorithm results define “test positivity” and physician chart review as the criterion standard (denominator). The e-EOL algorithm will be iteratively refined to improve its test operating characteristics. For the purposes of this project, assuring adequate specificity (80-90%) will be more important than optimal sensitivity (40-50%).

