**D.5.4. Statistical Analysis Plan:** We will use descriptive statistics to characterize study participants and proportion of intervention elements and follow-up assessments completed. The specificity and positive predictive value of the e-EOL algorithm operating in real world practice will be assessed using methods described for Aim 1 with physician chart review as the criterion standard. Acceptability and feasibility process data will be tallied. The main decision making outcome will be *change in the stage of intent to discuss EOL care options* from baseline through all follow-up intervals. Movement to an adjacent stage is a 1 point change. We will assess several aspects of stage change based on the proportion of patients at each time interval showing: 1) *any* stage pro/regression, and 2) *full progression* to the action stage of discussion EOL care options. Mean and range of progression at each interval will also be reported. The proportions above and means for *persistent* change will also be defined as the difference between baseline and 6 months (or 3 months if no 6 month contact or patient deceased). We will similarly examine pre- and post-intervention changes over time in knowledge, attitudes, and beliefs about EOL care and prognosis, decisional conflict, and QOL using non-parametric tests among the intervention group versus controls. Pre-specified subgroup analyses will stratify change in outcomes by: condition, mistrust, and spirituality. To achieve sensitivity of around 50% (with 10% confidence intervals, e.g. CI: 40% to 60%) in the outpatient algorithm, we will need to review 150 charts of patients diagnosed with metastatic (Stage III or IV) breast, lung and colorectal cancer (75 “test positive” and 75 “test negative” cases). The controlled pilot study in Aim 3 is designed to establish: feasibility, acceptability, detect preliminary efficacy signals (changes in behavioral intent, knowledge, attitudes, beliefs, decisional conflict), and generate point/variance estimates to be used to in power calculations for a future fully-powered RCT. We propose a small pilot RCT that will include 24 patient-caregiver pairs in each arm (intervention versus a usual care control group). This will yield greater than 80% power to detect a large intervention effect defined as an absolute difference in desired primary outcome of 40% (across a range of different point estimates), and between 60-70% power to detect a more modest absolute difference of 30% between the two groups (across a range of point estimates). To ensure the ability to recruit the additional patient-caregiver pairs for the study, we will extend the enrollment period from 15 months to 18 months. Parkland Hospital providers care for more than 900 breast, lung and colon cancer patients per year, and roughly 40% are African American; consequently we believe that we will able to successfully enroll this number of participants within our 18 month timeframe.

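### Aim 1 specifies no separate charts, optimism correction or locked rule, so the reported sensitivity of the outpatient algorithm is likely to be too high

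*Combined protocol and SAP*

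**What the plan says.** The Specific Aims (5.1.E) state Aim 1 as validating the algorithm for outpatients. Section D.3 describes a search over rules: "We will explore the impact of different types of Boolean logic combining these factors". Physician chart review is the criterion standard, and "Sensitivity, specificity, and positive/negative predictive values for the algorithm will be calculated". The next step is that "The e-EOL algorithm will be iteratively refined to improve its test operating characteristics". The working targets in D.3 are specificity of 80-90% and, with lower priority, sensitivity of 40-50%.

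Section D.5.4 sizes the chart review on sensitivity, aiming for a value near one half with limits ten points either side. For that purpose the investigators write that "we will need to review 150 charts of patients diagnosed with metastatic (Stage III or IV) breast, lung and colorectal cancer". Half of these charts (75) are to come from patients whom the algorithm flags and half from patients whom it does not.

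The refined algorithm then runs on new patients in Aim 3 (D.5.1). D.5.4 adds: "The specificity and positive predictive value of the e-EOL algorithm operating in real world practice will be assessed". D.5.3 lists the same two accuracy measures, plus the number flagged, under feasibility. Sensitivity is in neither list. Nowhere does the plan give a development/validation split, fresh charts, cross-validation, bootstrap, a limit on iterations or a locked version for the Aim 1 estimates.

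**The concern.** When several rules are compared on one set of charts and the best is kept, part of its apparent advantage is chance. Its accuracy on those same charts is then optimistic. That is development, not validation.

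Sensitivity is the most exposed measure. It sets the size of the chart review, and no later step retests it. A rule could appear to reach the 40-50% target when it does not. The figure would then be carried into the planned manuscript and the larger trial that this work is meant to support.

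**Working it through.** **1. The plan's own figure.** Inputs from D.5.4: sensitivity p = 0.50, half-width h = 0.10. The confidence level is not stated, so 95% is assumed (z = 1.96).

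- Criterion-positive charts needed: z²p(1−p)/h² = 1.96² × 0.25 / 0.01 = 96.04.
- In the inpatient pilot (D.1), 64% of patients were criterion-positive: 96.04 / 0.64 = 150.06.

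This reproduces 150, although the plan does not state the 64% step. On this reading the ±10-point interval for one fixed rule uses up all 150 charts, and none remain for separate validation.

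**2. Optimism from choosing the best rule.** Assumptions: 96 criterion-positive and 54 criterion-negative charts; K equally good rules with true sensitivity 45% and specificity 88%; the rule with the highest sensitivity + specificity is kept; latent between-rule correlation 0.8 or 0; 4,000 runs. Mean apparent minus true value, in points:

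| Rules tried | Sensitivity, corr. 0.8 | Sensitivity, corr. 0 | Specificity, corr. 0.8 | Specificity, corr. 0 |
|---|---|---|---|---|
| 1 | about 0 | about 0 | about 0 | about 0 |
| 2 | +1.3 | +2.1 | +1.1 | +1.6 |
| 5 | +2.8 | +4.4 | +2.3 | +3.1 |
| 10 | +3.8 | +6.2 | +3.0 | +4.1 |
| 20 | +4.6 | +7.5 | +3.6 | +4.8 |

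Hand check at correlation 0:

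- Standard error of sensitivity: √(0.45 × 0.55 / 96) = 0.0508.
- Standard error of specificity: √(0.88 × 0.12 / 54) = 0.0442.
- Standard deviation of their sum: √(0.0508² + 0.0442²) = 0.0673.
- Expected excess in sensitivity: E(max of K standard normals) × 0.0508² / 0.0673 = E × 0.0383.
- With E = 1.16 for K = 5 this is 4.4 points; with E = 1.87 for K = 20 it is 7.2 points. Both are close to the simulation.

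**3. Effect of the 75/75 sampling.** The table treats the charts as a random sample, but the plan draws them by algorithm result. Take one fixed rule, no tuning, 64% criterion-positive, true sensitivity 45% and specificity 85%:

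- Criterion-positive among flagged: 0.64 × 0.45 / (0.64 × 0.45 + 0.36 × 0.15) = 0.288 / 0.342 = 0.842.
- Criterion-positive among unflagged: 0.64 × 0.55 / (0.64 × 0.55 + 0.36 × 0.85) = 0.352 / 0.658 = 0.535.
- Crude sensitivity with equal numbers: 0.842 / (0.842 + 0.535) = 61%, which is 16 points too high.
- Crude specificity: 0.465 / (0.465 + 0.158) = 75%, which is 10 points too low.

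Simulating rule selection on charts drawn this way, crude sensitivity stays about 10 to 16 points too high. Crude specificity is too low or near unbiased in most settings (about −3.5 points for the best of 5 rules at correlation 0.8). It is clearly too high only with many weakly correlated rules. When the charts are weighted back to the flagged and unflagged fractions, the sampling distortion goes and the selection optimism remains: about 3 to 7 points in sensitivity and 3 to 6 in specificity for the best of 5 to 20 rules.

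**4. Precision if charts are split.** With half the charts held out, 75 × 0.64 = 48 are criterion-positive and the half-width is 1.96 × √(0.25 / 48) = 14.1 points, before any effect of weighting.

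**The case against.** The plan does not say that each refinement reuses the same charts. It gives 150 as the number needed to estimate sensitivity, not as the tuning set, and D.3 also mentions practice reviews. This stands. The bias is conditional on reuse, and the plan is silent rather than explicit.

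Aim 3 reassesses specificity and PPV on new patients, and D.3 ranks specificity above sensitivity. This also stands for those two measures, although the number of unflagged charts to be reviewed, which specificity requires, is not given. It does nothing for sensitivity.

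The consequences are bounded. The treating physician confirms eligibility before enrolment (D.5.1), so a flag alone enrols nobody, and optimistic sensitivity does not bias the randomised comparison. D.3 itself is headed as refining the algorithm, although the Specific Aims call the work validation.

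A reader might infer three stronger things that the documents do not support:

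- *That reported specificity will also be too high.* The 75/75 sampling pulls crude specificity down, and the net direction depends on unstated features of the search.
- *That an error of 7 points or more from selection is typical.* That needs about 20 uncorrelated rules. The candidates share the same cancer and metastasis codes (Table 1), so strong correlation is more plausible.
- *That the confidence interval is too narrow.* The calculation shows a shift in where the interval is centred, not an error in its width.

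**Conclusion.** The concern holds for sensitivity. If the rule is chosen and reported on the same charts, selection alone is likely to overstate sensitivity by about 3 to 5 points for the best of 5 to 20 strongly correlated rules, and by up to about 7 if they are uncorrelated. This rests on an assumed number of rules, their correlation, equal true accuracy, and a criterion-positive share borrowed from the inpatient pilot. With a single prespecified rule it would be about zero. The shift is smaller than the planned 10-point half-width, but that half-width does not account for it, and no later step would reveal it.

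For crude specificity the direction of error is uncertain. Sampling by test result is a separate and, for crude sensitivity, larger distortion. Any correction for optimism must deal with it too: cross-validation without weights would simply preserve it.

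**What to change.** - List the candidate Boolean rules before chart review begins.
- Weight each reviewed chart back to the flagged and unflagged fractions of the source population, as defined by the algorithm version used to draw the charts.
- Estimate sensitivity, specificity and PPV by cross-validation or bootstrap that repeats the whole rule selection in each fold or resample, using the weights.
- Lock the rule before Aim 3 starts.
- If refinement has to be by hand, refine on one part of the charts, freeze the rule, and report only from the unused charts. Restate the precision: about a 14-point half-width for sensitivity if the charts are halved, subject to the weighting.

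The cost is a little more analysis and slightly lower reported accuracy, or wider intervals if the charts are split. No extra charts are needed. Only keeping ±10 points on untouched charts would require more, about 150 further charts by the calculation in step 1.

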#### **D.4. Details of Research Design and Methods for Aim 2: Refine components of a culturally sensitive intervention to improve knowledge of and intent to consider EOL care options.**

Use of decision aids, educational videos, and LHAs has been shown to be effective in improving medical knowledge and shared decision making and reducing racial disparities for several clinical conditions. Though there have been few applications of these promising approaches to palliative and EOL care, recent use of decision aids in improving knowledge about the goals of care for persons with advanced dementia, have shown promise. Aim 2 will iteratively refine the intervention messages delivered through a combination of novel DVD segments that we have developed, print materials, and guided discussions by a culturally concordant LHA. Through qualitative methods, including cognitive interviews, the team will test the language, framing, and communication strategies for conveying intervention messages and obtain feedback from primary care and oncology providers at Parkland Hospital to verify the appropriateness of these messages as intended by investigators. Participants for cognitive interviews will be recruited from the Community Research Registry database from the Health Topics Survey (STU# 112010-061, PI: [name] [name]) maintained by the Department of Clinical Sciences and be issued a \$15 gift card for participation.

**D.4.1. Continued Stakeholder Engagement and Eligibility Criteria for Oncology and Primary Care Provider Focus Group Participants:** The PI and research assistant will work to identify primary care physicians and oncologists who are eligible to participate in our focus groups. Eligible participants will: 1) identify as oncologists who specialize in treatment of breast, lung, prostate, and colorectal cancer, or 2) identify as primary care providers (Internal Medicine or Family Medicine), and 3) be employed at Parkland Hospital or one of its 12 COPCs. We aim to conduct two focus groups with 6-10 participants per group. Both focus groups will be audiotaped and transcribed, and will last 60 to 90 minutes. The PI has developed the focus group moderator guide that was used to obtain feedback on these novel DVD segments during focus groups conducted with geriatric and hospice and palliative medicine providers, and she has successfully completed a similar project the results of which were published in the *American Journal of Hospice and Palliative Medicine*. The goal will be to engage these important stakeholders and obtain their feedback with regard to the language, framing, and strategies they use in their discussions with AA patients and caregivers both to convey key health messages about EOL care options, as well as to overcome common stated or unstated reasons for resistance (including perceived conflict with religious beliefs and medical mistrust). In addition, we will get their reactions to the newly developed DVD and print educational materials about EOL options. All sessions will be audiotaped and transcribed.

**D.4.4. Analysis of Provider Focus Group Data:** Two members of the study team will analyze the content of the focus groups using standard qualitative methods approaches. They will perform in-depth, line-by-line coding of all the patient and provider transcripts using qualitative analysis software. A codebook of themes will be developed through an iterative process of coding, discussion, and recoding. Coding decisions will be compared, new themes identified, and areas of disagreement resolved through further discussion with the research team. Challenges and discrepancies will be discussed and resolved by the investigative team.

**D.4.5. Formative Approach to Building and Testing Intervention Components:** Based on our analysis of the previously conducted AA patient, caregiver, minister and hospice and palliative medicine provider interviews, we have created a matrix identifying the theory-based concepts to be addressed (e.g. spirituality), the key communication messages (e.g. palliative care is not against God's will), and the strategy for communicating it (e.g., video, counseling) [See Table 2]. We have developed a novel DVD that includes the key communication strategies described below.

**Table 2. Theoretical Constructs, Targeted and Associated Communication Messages, and**

Theoretical Construct	Communication Message	Intervention Strategy
Lack of Knowledge About EOL Care Alternatives	1) Palliative and curative care can be complementary. 2) Hospice and palliative care can help with pain, symptoms	1) Information session led by an AA LHA that includes: 2) DVD segments explaining EOL care options, including advance care planning, palliative care, and hospice care.
Conflict with Spiritual Beliefs	1) Advance care planning is not "giving up" or "losing faith." 2) Choosing palliative care /hospice is not going against God's plan.	1) Information session led by an AA LHA that includes: 2) DVD segments that address this conflict. (i.e., a testimonial from an AA clergy person with personal and/or professional experience in hospice/palliative medicine)
Mistrust in the Health Care System/Providers	1) Many AA patients have had positive experiences with hospice and palliative medicine and its providers.	1) Information session led by an AA LHA that includes: 2) DVD segments that address this construct (i.e., testimonials from current AA palliative care /hospice patients and/or testimonial from an AA physician with personal /professional experience with EOL care )

**D.4.6. Development and Testing of DVD Segments:** DVD segments have been created to: 1) address the perceived conflict between spiritual and religious beliefs and the hospice and palliative medicine philosophy of care, and 2) address AA patients' mistrust in the health care system. These new DVD segments combine text, voice-over-text narration, along with video testimonials of AA patients, physicians and religious leaders. To address the spirituality issues, AA clergy with experience with hospice and palliative medicine discuss their experiences with EOL care and how spirituality and EOL care philosophies can coexist without conflict. To address medical mistrust, we have included short video testimonials from an AA hospice patient and two AA caregivers of hospice patients who discussed their positive experiences with hospice care. Additionally, an AA hospice and palliative medicine physician and an African American palliative care nurse practitioner discuss their personal and professional experiences with EOL care. The videos were filmed without the use of prompts or stage directions to convey candid realism. The UTSW Medical Television group has done all filming and editing based on previously published filming and was guided by content input from [name], [name], and other content experts.

We have tested these DVD segments among community-dwelling African Americans who receive their care or serve as caregivers for patients who receive their care at UTSW, Parkland, and their affiliated outpatient clinics. We have obtained feedback from these participants to assess: 1) understandability of the materials; 2) how effectively the gist messages were communicated; 3) acceptability and cultural-sensitivity of the messages and materials. Given sensitivities about the perceived conflict between spirituality and choosing palliative care, we recruited focus group participants who were active members of their churches (including ministers). We have also presented the videos to the broader group of social scientists in [name] of Behavioral and Communication Sciences. Based on feedback from our primary care/oncology provider focus group, the segments will be iteratively refined, and re-evaluated as appropriate. This formative approach to intervention component development, testing, and refinement has been used successfully by Drs. [name] and others for a variety of behavior change trials.

**D.4.8. Culturally Concordant LHA/Coaching Model:** There is evidence for the value of combining 'health coaching' with a video or written health information and behavior change materials. A LHA is a 'health coach,' who will be a trained counselor who will introduce a topic to a patient and talk with them after viewing or reading standardized health information. This helps provide supplemental information tailored to the patient's individual clinical and personal situation, enables the patient to ask clarification questions, and provides moral, spiritual and motivational support for behavior change for patients and caregivers. The intervention we plan for Aim 3 will combine the DVD segments along with a face-to-face counseling session with a culturally concordant LHA with training in EOL care discussions. We will recruit an AA LHA from the community (preferably a prominent AA church or faith-based organization in Dallas) who, along with the PI, will undergo training in providing culturally sensitive EOL care counseling via the Respecting Choices® First Steps® ACP program. This rigorous, evidence-based program provides training for healthcare and community leaders in facilitation and effective communication about advance care planning. The LHA will be actively involved in script and intervention protocol development. The LHA will also attend sessions in the

Palliative Care Clinic, and will observe the palliative care providers as they conduct their clinic sessions. The LHA will do a progressive series of in-service work with the Parkland palliative care team and the PI to give them a chance to observe other experts engage patients in EOL care discussions, practice co-leading these discussions, and finally counseling individuals themselves. The PI will observe the LHA on several interactions and give them feedback until competency in this area is assured.

**D.5. Details of Research Design and Methods for Aim 3: Assess the feasibility and acceptability of a multifaceted EOL care behavior change pilot intervention.** The pilot intervention will combine the refined elements from Aims 1 and 2, to conduct a small pilot RCT comparing the intervention group to a usual care control group. All of these aims taken together lay the groundwork for a future, fully powered RCT.

**D.5.1. Study Subject Identification and Enrollment:** We will use the refined e-EOL algorithm in real-time to identify AA patients with Stage III or IV breast, lung, colorectal, prostate, or other advanced cancer for EOL care counseling. The e-EOL algorithm will run once every day to flag potentially eligible candidates using an IT protocol used successfully in previous intervention research at Parkland. The eligibility criteria are the same as those outlined in D.4.1. (AAs,  $\geq 21$  years, with advanced breast, lung or colon cancer, are English proficient, competent, cognitively intact by Mini-cog test, and no prior palliative care consult or receiving palliative care). Patients with earlier stage cancers (I and II) may be chosen for the intervention based on co-morbidities, functional status, or other factors that we deem appropriate. The research assistant will contact the patients' physicians to confirm eligibility and get permission to introduce the study to the patient. Once eligibility is confirmed, the research assistant will introduce the study to the patient, obtain informed consent, and administer the pre-intervention survey and needs assessment (described below). Each patient will be asked to identify a primary caregiver that will be able to participate in the intervention. Caregivers must be: 1) identified by the selected patient, 2)  $\geq 21$  years of age, 3) English proficient, and 4) competent to participate. The research assistant will then notify the EOL LHA of any study participants. The EOL LHA will contact each patient's primary caregiver by phone to confirm their participation in the study, and arrange a time to meet with both the patient and caregiver to conduct the intervention. We will recruit up to 60 patients and their caregivers, if a caregiver is available to participate, to allow us to pilot the intervention and sort out logistics of administering the intervention in a clinical setting prior to randomization. Overall, at least 48 patient-caregiver pairs will be randomized in the study representing an approximately even distribution across different cancer diagnoses. Twenty-four patient-caregiver pairs will be randomized to the intervention arm of the study, and twenty-four will be randomized to the usual care control group.

**D.5.2.a Description of the Pilot Intervention:** The EOL LHA will meet with eligible patients and their caregivers to tell them their doctor approved of them receiving more information about their treatment options. The LHA will then assist the eligible patients and caregivers in watching the EOL care DVD segments (the video modules described in Aim 2 targeted to their pre-intervention survey needs assessment). After the patients and caregivers watch the DVD, the LHA will answer questions and provide additional information. They will then use counseling scripts created by the PI and research team to probe in more depth the patient's goals of care, and understanding of their clinical condition, prognosis, and treatment options. They will tailor the discussion to the patient's values, preferences, concerns, and clinical circumstances. Those who express interest in hearing more about EOL care options will be encouraged to discuss this with their doctor. The counselor will offer to update their physician on their discussion and help communicate the patient's desire for a palliative care consult or advance directive (if that is something they wanted). After patients have viewed the intervention video, the LHA will follow up with patients the next business day to answer any questions that may have come up and inquire about the patient's thoughts regarding executing any advance care planning documents. As appropriate, the LHA will follow up again within one week to address questions or concerns and guide patients about how to complete documents and facilitate referrals, as needed. Specific questions about prognosis will be referred to the treating physician. Formal palliative care referrals will be ordered and performed in the usual fashion with the exception that the patient may ask the LHA to update the palliative care team on their prior discussions, concerns, and preferences. All intervention sessions will be audiotaped to ensure intervention fidelity. Patients randomized to receive the intervention will receive a \$20 gift card for their time and effort.

**D.5.2.b. Usual Care:** Participants randomized to usual care will proceed with clinical care as already routinely implemented by their physicians. At the time of recruitment, they will be asked to identify their primary caregiver who will also be contacted. Patient-caregiver pairs who are randomized to usual care will also be

asked if they would be willing to be contacted at 1, 3 and 6-month intervals to complete the post-study assessment. Participants in this group (as well as the intervention group) will be given a \$10 gift card after completing each of four surveys for their time involved with the study. All participants will be mailed a reminder letter that study staff will be contacting them to participate in follow-up surveys a couple of weeks prior to the 1-, 3-, and 6-month surveys. The reminder letter sent prior to the 1-month survey will include an informational brochure that briefly and simply summarizes advance care planning options.

**D.5.3. Study Measurements and Data Collection Strategy:** Table 3 outlines the primary and secondary patient outcomes and other measurements we will do at baseline, 1, 3, and 6 months of follow-up.

**Primary Outcomes:** Feasibility and acceptability are the main process outcomes. Feasibility is success in accurately identifying eligible patients via the e-EOL algorithm (number flagged, specificity, positive predictive value), and numbers and rates of patients completing the pilot intervention and follow-up interviews.

Acceptability will be measured with Likert scale items rating “understandability, informativeness, balance, right amount of information, helpfulness, and “recommending this to others” used in published trials of decision aids. We will also ask open-ended questions on things they did or did not like about the intervention. The primary decision making outcome is change in intent to discuss EOL care options based on the Transtheoretical Stages of Change Model, an approach used in many other realms. We will categorize patients into the following stages: 1) Pre-contemplation: is unaware of EOL care options/has not thought about discussing this with a provider; 2) Contemplation: is aware of EOL care options/thinking about discussing options; 3) Preparation: intends to discuss EOL care issues with the doctor/has a plan for talking about it; 4) Action: has a discussion with the provider about EOL care. The completion stage is not applicable in this medical situation because the goal of the intervention is for the patient to have an informed discussion about benefits and harms of all treatment options including EOL care. The intent is NOT to get all patients to choose palliative care or hospice, or complete and an advance directive, but for them to understand how palliative care may benefit them now or in the future, and how it can be combined with curative care. *The goal is for the patient to make “the right decision for them” based on knowing all of the facts and options.*

**Secondary Outcomes** we expect to be changed will also be measured. 1) Knowledge of prognosis and EOL care options: will be measured by a questionnaire from prior NCI-funded palliative care studies; 2) Decisional conflict will be assessed by the Decisional Conflict Scale, a validated 16 item scale measuring uncertainty about the best course of action and factors contributing to uncertainty. Scores <25 (on this 100-point scale) are associated with implementing decisions, and scores >38 with decisional delay; 3) Quality of life (QOL): will be assessed with the McGill QOL Questionnaire, a well-validated 20-item scale developed to measure QOL at the EOL; 4) Healthcare utilization will include: outpatient visits (incl. palliative care), ED visits, hospitalizations, total hospital days, and use of hospice services (type and time to hospice initiation); 5) We will also record the date and place (hospital, hospice, home) of deaths within a 6 month follow-up period.

**Other Patient and Treatment Variables** will be measured to inform exploratory subgroup and effects mediation analyses such as: 1) Sociodemographics: age, race/ethnicity, gender, education, marital status, religious preference, insurance, income, social support; 2) Clinical and treatment data: cancer type and stage, ECOG performance status, reason for admission, advance directive status, inpatient and outpatient provider details (specialty, presence of a primary care provider, usual source of care), and discharge plan and location; 3) Health literacy as measured by the Cancer Health Literacy Test \* 4) Spirituality: will be measured by the Brief RCOPE measurement tool, a 14-item measure of religious coping with major life stressors that is commonly used to measure of religious coping for research purposes.

